6.3. Other Efficacy Endpoints

- Changes from Baseline in:
 - PANSS total score and subscale scores (positive, negative, and general psychopathology)
 - CGI-S score
 - BNSS total score
 - MADRS total score
 - ESS total score
 - BACS composite score
 - UPSA-B total score
 - SLOF total and subscale scores
 - EQ-5D-5L visual analog scale (VAS), index score and dimension score
 - MSQ score
- Time to relapse, rate of relapse, and frequency of hospitalization due to relapse. Relapse will be defined as the earliest occurrence of any of the following:
 - Worsening of > 30% PANSS total score from Baseline and CGI-S > 3
 - Hospitalization for worsening of psychosis

- Emergence of suicidal ideation, homicidal ideation and/or risk of harm to self or others
- Discontinuation from the study due to exacerbation of the underlying illness of schizophrenia
- Time to all cause discontinuation from the study
- Change from Baseline in tobacco use
- Plasma cotinine concentrations

6.4.

CCI

[figure not shown]

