At Baseline (Day 1), subjects who have successfully completed the washout of psychotropic medications and have met the eligibility criteria will be randomly assigned via interactive web response system (IWRS) to SEP-363856 or quetiapine XR treatment groups in a 2:1 ratio. Study drug dosing will begin the evening of the Baseline visit. Treatment will continue once-daily, in the evening at bedtime, for the remainder of the Treatment Period, during which the procedures outlined in [Table 2](#) will be conducted. Subjects will be seen at Baseline, Weeks 1, 2 and 4, and then every 4 weeks thereafter up to Week 52. Telephone calls will be made by a member of the clinical research staff to the subjects weekly between visits that are more than one week apart to collect AEs and concomitant medications, as well as to remind subject about adherence to study drug administration and upcoming visits.

Subjects may be hospitalized for the first 7 days of the Treatment Period, if deemed clinically necessary by the Investigator. Further hospitalization during the Treatment Period will require approval from the Medical Monitor.

Subjects randomized to the SEP-363856 group will receive SEP 363856 50 mg/day from Day 1 through Day 3 and 75 mg/day from Day 4 through Day 7. Beginning on Day 8, the dose can be adjusted among 3 dose levels (50, 75 and 100 mg), as deemed clinically appropriate by the Investigator.

Subjects randomized to the quetiapine XR group will receive quetiapine XR 300 mg/day on Days 1 and 2, 400 mg/day on Days 3 and 4, and 600 mg/day from Day 5 through Day 7.

Beginning on Day 8, the dose can be adjusted among 3 dose levels (400, 600, and 800 mg), as deemed clinically appropriate by the Investigator.

Dose adjustments made to either SEP-363856 or quetiapine XR will be done in a blinded fashion.

Dose increases can be made no more frequently than weekly to the next higher dose level beginning on Day 8, if the response to the previous dose level is not adequate and there are no significant tolerability problems, based on Investigator judgement. Increases in dose will occur at regularly scheduled study visits, when possible. However, dose increases between regularly scheduled visits may occur (as long as subject have been taking the previous dose level for at least 7 days). If a dose increase is performed between regularly scheduled visits, subjects will be required to return to the clinic at an unscheduled visit for drug dispensation.

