16.2.12. RELAPSE

Relapse is defined as the earliest occurrence of any of the following:

- Worsening of >30% PANSS total score from Baseline (Day 1) and a CGI-S score >3
- Hospitalization for worsening of psychosis
- Emergence of suicidality, homicidality and/or risk of harm to self or others
- Discontinuation from the study due to exacerbation of the underlying illness of schizophrenia.

PANSS and CGI-S assessments taken at both scheduled and unscheduled visits will be considered when identifying the relapse event. The percent change in PANSS total score from Baseline will be calculated as described in [Section 16.1.6](#). Occurrence of hospitalization for worsening of psychosis will be identified by medical review of the data collected on the “*Psychiatric Hospitalization*” CRF page as well as the SAEs prior to database lock. Emergence of suicidality, homicidality, and/or risk of harm to self or others will be identified as outlined in [APPENDIX 11](#). Discontinuation from the study due to exacerbation of the underlying illness of schizophrenia will be identified as an AE included in the SMQ search listed in [APPENDIX 13 that has action taken = “Drug Withdrawn”](#).

The evaluation period for relapse will be from the day of the first dose of study medication to 2 days after the day of the last dose of study medication.

The date of relapse is defined as the earliest of: the start date of the assessment at which the qualifying PANSS and CGI-S data were collected, the date of hospital admission for worsening of psychosis, the

Document: **CCI**

Author: **PPD**

Version Number: 0.6

Version Date: 30JAN2023

Template No.: CS_TP_BS016 Revision 6

Reference: CS_WI_BS005

Effective Date: 02Dec2019

date of the assessment at which a qualifying C-SSRS event is identified, the start date of the qualifying adverse event for the second and third criteria, and the last dose date for the fourth criterion.

Time-to-relapse (in days) is defined as the date of relapse – the first dose date + 1. Subjects completing/discontinuing from the study without meeting the criteria for relapse will be censored on 2 days after the last dose of study medication.

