APPENDIX 2. PARTIAL DATE CONVENTIONS

The actual dates as collected on the CRF will be presented in the listings. Imputed dates will not be presented in the listings unless otherwise specified.

ALGORITHM FOR ADVERSE EVENTS:

As a general rule, if the start date of an AE is available and the start time of the AE is not available, the AE will be considered to have started after the study drug dose administered on the day of the AE start date.

In case of partial or missing AE start and/or end dates, impute partial or missing event start and/or end dates (if not ongoing) using the algorithm below. If an AE has some missing components in both the start and end dates, first impute the end date.

AE end date imputation

- If year and month (YYYY-MM) of AE end date are known, then impute the missing day part to be the last day of the month.
- If only year (YYYY) of AE end date is known, then impute the missing month and day part to be 31st December.

If AE end date is completely missing and AE is not ongoing, then impute AE end date to date of last contact.

AE start date imputation

- If year and month (YYYY-MM) of AE start date are known and YYYY-MM = year and month of 361-304 study med start date, then impute AE start date to the earlier of 361-304 study med start date and AE end date (if non-missing).
- If year and month (YYYY-MM) of AE start date are known and YYYY-MM ≠ year and month of 361-304 study med start date, then impute AE start date to YYYY-MM-01.
- If only year (YYYY) of AE start date is known and YYYY = year of 361-304 study med start date, then impute AE start date to the earlier of 361-304 study med start date and AE end date (if non-missing).

Document: CCI

Author: PPD

Version Number: 0.6

Version Date: 30JAN2023

Template No.: CS_TP_BS016 Revision 6

Reference: CS_WI_BS005

Effective Date: 02Dec2019

- If only year (YYYY) of AE start date is known and YYYY ≠ year of 361-304 study med start date, then impute AE start date to YYYY-01-01.
- If AE start date is completely missing, then impute AE start date to the earlier of 361-304 study med start date and AE end date (if non-missing).

Using the full or imputed event dates, assign events into pre-treatment events vs. AE as described below.

If both event start date/time and 361-304 study med start date/time are available:

- If event start date/time < 361-304 study med start date/time, then pre-treatment event.
- If event start date/time ≥ 361-304 study med start date/time, then AE.

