APPENDIX 11. IDENTIFICATION OF SUICIDALITY, HOMICIDALITY, AND/OR RISK OF HARM TO SELF OR OTHERS

Condition	Data Source	Criteria
Suicidality or Risk of Harm to Self	Adverse events	
 AEs with preferred term of “Assisted suicide”, “Completed suicide”, “Suicide attempt”, “Suspected suicide”, or “Suspected suicide attempt” Medical review of all AEs contained in the MedDRA SMQ of “Suicide/self-injury (SMQ)”
	C-SSRS	
 C-SSRS findings of at least one occurrence of suicidal ideation (Item 4 and/or Item 5) or at least one occurrence of suicidal behavior C-SSRS findings of self-injurious behavior, defined as a “Yes” answer to the following question in the Suicidal Behavior section: Has subject engaged in Non-Suicidal Self-Injurious behavior?
Homicidality or Risk of Harm to Others	Adverse events	
 AEs with preferred term of “Aggression”, “Anger”, “Antisocial behaviour”, “Belligerence”, “Defiant behaviour”, “Homicide”, “Homicidal Ideation”, “Hostility”, “Physical abuse”, “Physical assault”, or “Violence-related symptom” contained in the MedDRA SMQ of “Hostility/aggression (SMQ)” AEs with a verbatim term that contains text of “homicid*”, “kill*”, or “murder*”.

Document: CCI

Author: PPD

Version Number: 0.6

Version Date: 30JAN2023

Template No.: CS_TP_BS016 Revision 6

Reference: CS_WI_BS005

Effective Date: 02Dec2019

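### SAP 16.2.12 dates a hospitalisation relapse at adverse-event onset when that precedes admission, and its window does not exclude the pre-dose Visit 2 C-SSRS

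*SAP*

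**What the plan says.** Protocol 6.3 and SAP 16.2.12 list four relapse criteria. The second is "Hospitalization for worsening of psychosis". SAP 16.2.12 finds these cases by medical review of the psychiatric hospitalisation CRF page and of SAEs before database lock.

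For dating, the SAP states "The date of relapse is defined as the earliest of: the start date of the assessment" with the qualifying PANSS and CGI-S data. It then adds "the date of hospital admission for worsening of psychosis", the date of a qualifying C-SSRS assessment, and "the start date of the qualifying adverse event for the second and third criteria, and the last dose date for the fourth criterion". Time to relapse is the relapse date minus the first dose date plus 1.

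On the window, SAP 16.2.12 says "The evaluation period for relapse will be from the day of the first dose of study medication" and closes it 2 days after the day of last dose. No clock time is mentioned. Protocol 7.1 says "Study drug dosing will begin the evening of the Baseline visit". SAP 17.6.1 requires the Visit 2 C-SSRS to be pre-dose if it is to serve as Baseline.

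SAP Appendix 11 lets criterion 3 be met by "C-SSRS findings of at least one occurrence of suicidal ideation (Item 4 and/or Item 5) or at least one occurrence of suicidal behavior", and also by a positive answer on non-suicidal self-injury. It does not say that the assessment must follow the first dose.

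**The concern.** A worsening recorded as an AE does not by itself meet any relapse criterion; under criterion 2 it becomes a relapse when the subject is admitted. Taking the earlier of onset and admission uses a later event to classify an earlier day. It also leaves the criteria on different clocks, because criterion 4 uses last dose date whenever the exacerbation began.

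The second gap concerns which data may count. Sections 6.2, 17.1 and 17.6.1 of the SAP separate pre-dose from post-dose data, and 6.2 and 17.1 use clock time where it is available. Section 16.2.12 and Appendix 11 do not, so behaviour that preceded any study drug could be counted as a relapse on it.

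At stake are the time-to-relapse curve and log-rank test and, through the window, the count behind the relapse rate. The primary safety endpoint is not involved.

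**Working it through.** The documents give no relapse rate, event count, power or onset-to-admission gap, so there is no planned figure to reproduce. The check applies the SAP's own rules to worked records.

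**Inputs**
- Relapse date: earliest of the listed dates (SAP 16.2.12).
- Time to relapse = relapse date − first dose date + 1, which equals the study day.
- Window: day of first dose to day of last dose + 2 (SAP 16.2.12).
- Hospitalisation is a seriousness criterion (Protocol 12.1.2), so an AE record with a start date will normally exist.
- Planned arms: 300 × 2/3 = 200 and 300 × 1/3 = 100.

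**1. Back-dating under criterion 2**

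| AE onset | Admission | SAP date | Admission date | Shift (days) |
|---|---|---|---|---|
| Day 50 | Day 50 | 50 | 50 | 0 |
| Day 50 | Day 57 | 50 | 57 | 7 |
| Day 50 | Day 64 | 50 | 64 | 14 |
| Day 50 | Day 71 | 50 | 71 | 21 |

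Once onset comes first, the admission date has no effect.

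**2. Comparison with criterion 4.** Two subjects worsen on Day 50. One is admitted on Day 64 and is dated Day 50. The other is withdrawn for the exacerbation with last dose on Day 64 and is dated Day 64. The onset is the same, and the relapse dates differ by 64 − 50 = 14 days.

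**3. Edge of the window.** Last dose Day 100, so the window closes on Day 102. With AE onset Day 101 and admission Day 105, the SAP date (101) is inside and the admission date (105) is outside. The event count, not only its timing, depends on which date is used.

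**4. Visit 2 C-SSRS.** The assessment is on Day 1, before the evening dose, and asks about the time since the last visit. Exclusion criterion 4 removes Items 4 and 5 at Baseline. Exclusion criterion 6 looks back from Screening, so it does not cover Screening to Day 1. What remains is suicidal behaviour or non-suicidal self-injury in that interval. Time to relapse = 1 − 1 + 1 = 1. If every randomised subject is in the efficacy population, each case adds 1/200 = 0.5 point or 1/100 = 1.0 point to the arm's relapse rate.

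**5. Size under assumptions, none of them from the documents**
- *Log-rank.* Simulated 200 versus 100 subjects, 20% one-year relapse, half by admission, mean gaps of 7, 14 or 28 days equal in both arms, 50% dropout, hazard ratio 1 or 0.6. The mean absolute change in the log-rank Z was below 0.02, and the 5% decision changed in under 1% of runs.
- *Window, deliberately generous.* One 200-subject arm, about 30% one-year risk, every relapse an admission, 40% completing (80/200), and onset deciding whether an event is in the window. The Kaplan-Meier one-year risk was 30.1% with no gap, and 30.5%, 31.1% and 32.2% with mean gaps of 7, 14 and 28 days. Mean events rose from 40.6 to 41.5, 42.6 and 44.9.

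**The case against.** The protocol says which events are relapses but gives no dating rule, so the SAP does not contradict it. Hospitalisations come from two sources, one with an admission date and one with an AE start date, and the list may have been meant as one date per source. Onset may also lie closer to the clinical relapse than admission, which depends on logistics. The rule is pre-specified and identical in both arms, and composites often date their components differently. For the C-SSRS, the SAP's word emergence, the Baseline definition in 17.6.1, exclusion criterion 5 (significant risk of harm, on investigator judgement) and eligibility adjudication all suggest that a pre-dose finding was neither intended nor likely.

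Most of this limits the size. It does not remove the defect. The text says earliest, and not one date per source; it defines the event as the hospitalisation and gives no reason for preferring onset. If onset were the intended clock, criterion 4 would be expected to follow it. The C-SSRS case is rare, but nothing in 16.2.12 or Appendix 11 excludes it.

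Three stronger readings are tempting and not supported:
- *The Kaplan-Meier quartiles move.* At an assumed 20% relapse even the 25th percentile is not expected to be reached, and the median among relapsers only is not a planned output.
- *An SAE with no start date becomes a Day 1 relapse.* Appendix 2 does say "If AE start date is completely missing, then impute AE start date to the earlier of 361-304 study med start date and AE end date", but it applies the imputed date to classifying events as pre-treatment or AE and to assigning dose at onset. Section 16.2.12 does not call on it, and a serious event with a known admission and no start date would be unusual.
- *Relapses in general are dated too early.* PANSS/CGI-S and C-SSRS events are dated at the assessment, and for a criterion 3 AE the start date is the event itself. Back-dating ahead of the defining event is confined to criterion 2.

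**Conclusion.** The point holds for criterion 2 and for the opening of the window. Followed literally, SAP 16.2.12 dates a hospitalisation relapse before the hospitalisation whenever AE onset precedes it, by exactly the onset-to-admission gap. It can also bring in an event whose admission is more than 2 days after last dose. A qualifying pre-dose Visit 2 C-SSRS would count as a Day 1 relapse.

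The total effect cannot be computed, because the documents give neither the gap nor the frequency of Day 1 findings. The expectation of little change in the log-rank test rests on gaps being similar in the two arms; the documents give no reason to expect otherwise. Protocol 15.3.5 makes all efficacy analyses exploratory and SAP 7.4 reports nominal p-values, so the priority is low. The case for acting is that the rules as written would misdate or miscount some events and are easy to correct.

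**What to change.** In SAP 16.2.12:
- Date criterion 2 by hospital admission. Use the observed AE start date only if the admission date is missing.
- Use AE start for criterion 3 events found through AEs.
- State that imputed AE start dates do not set relapse dates.
- Require qualifying data to follow the date and time of first dose, and state there and in Appendix 11 that Visit 2 assessments are ineligible.

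The cost is SAP wording and programming; no new data are needed. Time to relapse becomes slightly longer. A few admissions more than 2 days after last dose will no longer count under criterion 2, and this should be disclosed. Some of them will still be captured by criterion 4: with onset Day 95, last dose Day 100 because of the exacerbation, and admission Day 105, the event stays in and its date moves from Day 95 to Day 100.

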10.3.2. Prohibited Medications

Psychotropic medications and medications with a propensity for psychotropic effects are not permitted during the Treatment Period, except for the medications discussed in [Section 10.3.5](#). Use of psychotropic medications is permitted after the last dose of study medication provided they are not administered prior to the final PANSS assessment.

The use of herbal supplements, dietary supplements or other complementary or alternative medications for treating psychiatric indications are not permitted during the Treatment Period; however, they are permitted after the last dose of study medication provided they are not administered prior to the final PANSS assessment.

Subjects who are administered a psychotropic medication (other than the study drug and the acceptable medications discussed in Section 10.3.5) for the purposes of treating an exacerbation of symptoms associated schizophrenia or due to lack of efficacy of the study treatment will be discontinued from the study.

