13. TERMINATION OF SUBJECT FROM STUDY/DISCONTINUATION OF STUDY DRUG

13.1. Criteria for Subject Termination

Subjects may be discontinued from study participation / the study drug at any time for any of the following reasons. The possible reasons for termination of study participation / study drug are as follows:

- Adverse event
- Lack of efficacy (specify; eg, no improvement in underlying condition)
- Lost to follow-up (specify)
- Withdrawal by subject (specify)
- Non-compliance with study drug (specify)
- Protocol deviation (specify)
- Death
- Pregnancy
- Other (specify)

If at any time during the course of the study, in the opinion of the Investigator, the subject may no longer safely participate due to a change in medical status (eg, experiences an AE, becomes pregnant), the subject must be discontinued from the study drug. Subjects discontinued from study drug will be discontinued from the study.

The reason for study drug discontinuation will be recorded on the appropriate CRF. In case of death, the date of death should be captured on the CRF.

Subjects who prematurely terminate the study participation will not be replaced.

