6.4. RETESTS, UNSCHEDULED VISITS, AND EARLY TERMINATION DATA

In general, for by-visit summaries, data recorded at the planned visits where assessment is intended to be given and collected within 9 days post last dose will be presented, as well as the derived Baseline value and the LOCF value.

Unscheduled measurements will not be included in by-visit summaries as a separate time point. Unscheduled measurements collected prior to the first dose of study medication will contribute to the derivation of the Baseline value. Unscheduled measurements collected post Baseline up to and including 9 days after the last dose of study drug will contribute to the derivation of the LOCF value, the potentially clinically significant (PCS) value, and the best/worst case value where required (e.g. shift table).

In the case of a retest, the assessment recorded under the planned visit will be used for by-visit summaries, and the assessment(s) recorded under unscheduled visit(s) will be presented in listings only.

As per protocol, study Visit 17 can be a Week 52/End of Treatment (EOT) visit or an Early Termination (ET) visit. If a subject terminates early, his/her measurements taken at the ET visit and within 9 days post the last dose will be mapped to the next planned visit (after the last scheduled visit the subject attended)

Document: CCI

Author: PPD

Version Number: 0.6

Version Date: 30JAN2023

Template No.: CS_TP_BS016 Revision 6

Reference: CS_WI_BS005

Effective Date: 02Dec2019

during which that assessment was expected to be performed as specified by the Schedule of Assessments table in the protocol. This applies to both efficacy and safety data. ET measurements taken beyond 9 days post the last dose will not be mapped.

Listings will include scheduled, unscheduled, retest, and early discontinuation data without regard to the 9-day window, with original dates and visits displayed.

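### Relapse by discontinuation is found only through one adverse-event coding, so a confirmed exacerbation exit without that coding can be censored as relapse-free; the 2-day relapse window also differs, unexplained, from the SAP's 9-day rules

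*SAP*

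**What the plan says.** Relapse is the earliest of four events: (1) a PANSS total rise of more than 30% with CGI-S above 3; (2) admission for worsening psychosis; (3) suicidality, homicidality or risk of harm; (4) leaving the study because the schizophrenia has worsened.

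For criterion 4, SAP 16.2.12 states: "Discontinuation from the study due to exacerbation of the underlying illness of schizophrenia will be identified as an AE included in the SMQ search" in Appendix 13, and it adds that the action taken must be drug withdrawn. Such an event is dated at the last dose. The evaluation period runs "from the day of the first dose of study medication to 2 days after the day of the last dose of study medication". For everyone else: "Subjects completing/discontinuing from the study without meeting the criteria for relapse will be censored on 2 days after the last dose of study medication".

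The protocol describes more than this. Section 15.3.5 has relapse identified by program and by manual review of the data. Section 13.1 lists, separately from adverse event, the termination reason "Lack of efficacy (specify; eg, no improvement in underlying condition", with free text. Section 10.3.2 says that subjects given a non-permitted psychotropic "for the purposes of treating an exacerbation of symptoms associated schizophrenia or due to lack of efficacy of the study treatment will be discontinued".

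Elsewhere the SAP works to 9 days after the last dose: the EFF population (5.2), LOCF (6.3), the general cut-off (6.5) and early-termination data, where "his/her measurements taken at the ET visit and within 9 days post the last dose will be mapped to the next planned visit".

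**The concern.** The endpoint is a reason for leaving the study, but the rule reads only one AE coding. A subject can leave because of exacerbation and be recorded under lack of efficacy or protocol deviation. Alternatively, the AE can be flagged as causing study discontinuation (SAP 17.1.6) while its action taken is something other than drug withdrawn. If no other criterion is met by day +2, that subject is censored at about the time of worsening and counted as a non-relapser in the crude rate. Censoring of that kind depends on prognosis, so the Kaplan-Meier estimate and the log-rank comparison lose their usual justification.

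The shorter window adds a second mismatch: a rating can be good enough for the PANSS analyses and for entry to the relapse denominator, yet be barred from counting as a relapse.

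Maintenance of efficacy, including relapse, is a stated objective (protocol 5.3), and SAP 16.2.12 tests it between arms.

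**Working it through.** **1. Sources for criterion 4.** The documents provide for five: the Appendix 13 AE with drug withdrawn; the disposition reason and its text (protocol 13.1); withdrawals under protocol 10.3.2; the AE field for study discontinuation (SAP 17.1.6); and manual review (protocol 15.3.5). SAP 16.2.12 uses the first only. It assigns medical review to admissions, and Appendix 11 assigns it to some self-harm AEs; criterion 4 gets none. The tracker that asks whether a psychiatric AE reflects the underlying illness (SAP 17.1.13) is only listed. SAP 3.7 mentions neither the AE-only rule nor the 2-day limit.

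**2. How the rules classify particular exits.**

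| Exit | Result under SAP 16.2.12 |
|---|---|
| Exacerbation, Appendix 13 AE, drug withdrawn | Relapse at last dose |
| Exacerbation in the disposition text, no such AE, ET rating by day +2 meets criterion 1 | Relapse |
| Same, but no criterion met by day +2 | Censored at day +2; non-relapser in the rate |
| Same, first qualifying ET rating on day +5 | Censored at day +2, while the rating enters the PANSS analyses |
| Lack of efficacy meaning only no improvement | Not a relapse, correctly |
| Admission on day +4 | Unclear: may count if its AE began by day +2, or through criterion 4 |

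The last row is open because the relapse date can be an admission date or the start of the qualifying AE, and the SAP does not say which of these must fall inside the window.

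**3. What criterion 1 can catch.** By SAP 16.1.6 the percentage change divides by baseline minus 30, so the rise must exceed 0.30 × (baseline − 30): 15 points at baseline 80, 12 at 70, 9 at 60 and 6 at 50. An ET visit within the planned 48 hours can therefore catch some exacerbations that have no AE.

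**4. Days 3 to 9.** The follow-up visit is at 7 ± 2 days, that is days 5 to 9. It has a C-SSRS but no PANSS or CGI-S (protocol 11.7.18). Its C-SSRS counts in the suicidality summaries (SAP 17.6.1) but always falls after the relapse window. Late PANSS and CGI-S ratings can come only from a late ET or Week 52 visit or from an unscheduled visit.

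**5. Size, for illustration only.** No relapse rate or dropout rate is stated. The sample-size text gives 300 × 2/3 = 200 on SEP-363856 and about 80 completers, so 200 − 80 = 120 early stops (60%). If an assumed share f of these are missed relapses, the crude-rate shift is 120f/200:

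- f = 2%: 2.4 subjects, 1.2 points
- f = 5%: 6 subjects, 3 points
- f = 10%: 12 subjects, 6 points
- f = 20%: 24 subjects, 12 points

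With constant hazards and 60% of the arm leaving by Day 365, the Kaplan-Meier relapse probability is 1 − 0.40^(r/0.60), where r is the fraction of the arm counted as relapsing. If 20% are captured it is 26.3%; counting a further 3%, 6% or 12% of the arm gives 29.6%, 32.8% or 38.7%. If 10% are captured it is 14.2%, against 18.0%, 21.7% or 28.5%.

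The denominator of 200 is randomised subjects; the SAP's rate uses the EFF population, which may be smaller.

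**The case against.** The AE route is wide. Protocol 12.1.1 counts exacerbation of an existing condition as an AE, 12.3 requires every AE to be recorded, and Appendix 13 holds both narrow and broad terms. In the sponsor's extension study, schizophrenia was among the most common AEs (protocol 4.2). An exacerbation withdrawal with no AE would then be a recording failure, and the share missed could be near zero. This stands as a limit on size. It does not explain why criterion 4 ignores the disposition record, or an AE flagged as causing study discontinuation with another action taken.

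The 2-day window is a defensible on-treatment choice. It matches the 48-hour ET visit, SAP 6.5 allows stated exceptions to the 9-day rule, and protocol 10.3.2 permits other psychotropics once drug has stopped and the final PANSS is done, so days 3 to 9 may mix withdrawal effects with new treatment. This stands, and it is why 9 days should not simply become the main window. What is missing is a stated reason.

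A reader might infer that every lack-of-efficacy withdrawal without an AE is a lost relapse. The documents do not support that: criteria 1 to 3 still apply to day +2, and the protocol's own example of lack of efficacy is absence of improvement. A reader might also infer that an admission on days 3 to 9 is always excluded; the dating rule leaves that open.

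**Conclusion.** The point holds as a gap in the definition of criterion 4 and an unexplained difference between windows. A confirmed exacerbation exit without the required AE coding, meeting no other criterion by day +2, is treated as relapse-free, and this can only lower the estimated relapse frequency. The amount cannot be calculated from the documents; the shifts shown rest entirely on assumed shares and on the implied 60% early stopping. Nor do the documents show which arm would gain, so a claim that the comparison is tilted towards one drug is not supported.

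The consequence is bounded. The protocol calls all efficacy analyses exploratory, p-values are nominal, and the primary safety endpoint does not depend on relapse. These subjects also remain visible in the disposition tables and in the PANSS plots by reason for stopping (SAP 16.1.1.2). It is worth correcting because the data are already collected and the correction is cheap.

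**What to change.** 1. Before unblinding, add to criterion 4 in SAP 16.2.12 a blinded review of the disposition reason with its specify text, withdrawals under protocol 10.3.2, and Appendix 13 AEs marked Yes for causing study discontinuation. Count only those confirmed as exacerbation and date them at the last dose. Do not count lack of efficacy that is only absence of improvement.
2. Keep the 2-day window as the main analysis. Add a sensitivity analysis extending criteria 1 to 3 and the censoring date to 9 days after the last dose. SAP 16.2.12 resets late events under criteria 1 to 3, and late censoring, to Day 365; adapt this so that completers' off-drug events are not moved back to Day 365 and counted as 52-week relapses.
3. State whether the window applies to AE onset or to admission.
4. List the AE-based rule and the 2-day window in SAP 3.7.

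Cost: SAP wording, some extra records in the medical review already planned before database lock, and one additional analysis; no new data. The 9-day result needs cautious reading, because days 3 to 9 may reflect stopping the drug or starting another.
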